## 2 OBJECTIVES

### 2.1 Primary Objective

The primary objective of the study is to evaluate a dose-response signal of IFX-1 in subjects with HS according to the HiSCR at Week 16.

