## 10 STATISTICAL METHODS AND DETERMINATION OF SAMPLE SIZE

### 10.1 General Considerations

A detailed statistical analysis plan will be developed and finalized (approved with signatures) before the Blind Data Review Meeting (BDRM), and may be amended after the BDRM and before unblinding the study database if the need arises.

The statistical analysis plan will include the exact definition of endpoints and variables to be analyzed, extensive details of the statistical analysis methods to be used together with the structure of tables and figures to be included as end-of-text tables and figures as well as appended listings for the clinical study report.

All endpoints and variables will be adequately evaluated. Individual data will be listed. Data will be summarized using suitable descriptive statistics; depending on the structure of the data, either sample statistics or frequency tables will be used. Data will be analyzed by cohort and study period (Main Period and Extension Period) and might be further differentiated (e.g., by visit or by study site).

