### 10.2 Determination of Sample Size

The primary efficacy endpoint will be analyzed using the multiple comparisons procedure-modelling (MCP-Mod) procedure [26-28]. A total of 175 subjects are planned to be

---

enrolled into the study (i.e., 35 subjects per cohort) to achieve at least 29 subjects per cohort available for the primary analysis of the primary efficacy endpoint.

The sample size is selected in a way that the multiple contrast test exceeds a power of 90%. With the planned sample size, the power criterion of the multiple contrast test is fulfilled because 29 subjects per cohort would yield a power of at least 90% to detect a dose-response signal if present. In this context, the HiSCR at Week 16 is assumed to be 25% in the placebo group, as shown in earlier HS studies [15], and 30%, 45%, 55%, and 60% in the active cohorts (Cohorts 2 to 5), with cumulative doses of 2000 mg, 4800 mg, 8000 mg, and 10,800 mg, respectively. A 1-sided significance level of  $\alpha = 0.025$  will be used.

Additionally, simulations were conducted to investigate the expected length of the 2-sided 90% confidence intervals (CIs) for the minimum effective dose (MED) and the median effective dose (ED50). Definitions of MED and ED50 can be found in Section 10.5. Based on the planned sample size of at least 29 evaluable subjects per cohort, wide 90% CIs can be expected for the MED and the ED50. The expected length of the 90% CIs was determined by simulations of the modelling step of the MCP-Mod procedure. To determine the true HiSCR at Week 16, a maximum possible effect for the agonist (Emax) model and a logistic model were selected, which are the same models that will be used as candidate models in the MCP-Mod procedure. A guesstimate of ED50 = 3000 was used for the Emax model and guesstimates of ED50 = 3500 and  $\delta = 1100$  was used for the logistic model.

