## 10.5 Analysis of Endpoints

### 10.5.1 Efficacy

The primary efficacy endpoint HiSCR at Week 16 will be analyzed using the MCP-Mod procedure. The MCP-Mod approach will include Hurley Stage at baseline, concomitant use of antibiotic therapy, and AN count at baseline as covariates.

---

Multiple contrast tests, which are part of the MCP-Mod procedure, will be used to test for a dose-response signal using the placebo cohort and the cohorts based on cumulative doses of 2,000 mg, 4,800 mg, 8,000 mg, and 10,800 mg as dose levels.

In the MCP-Mod procedure, dose-response models can be consistently considered as:

$$f(d, \theta) = \theta_0 + \theta_1 \cdot f^0(d, \theta^*),$$

where  $d$  denotes the respective dose, and  $f^0(d, \theta^*)$  denotes the standardized dose-response model parametrized by the vector  $\theta^*$ . In this parametrization,  $\theta_0$  denotes the location parameter,  $\theta_1$  denotes the scale parameter, and  $\theta^*$  determines the shape of the model function. For this study, a candidate set of 2 dose-response models are prespecified,  $m = 1, 2$ , which both characterize a monotonically increasing dose-response relationship:

1.  $E_{\max}$  model
2. Logistic model

For each of the standardized dose-response models  $f_m^0(d, \theta^*)$ , ( $m = 1, 2$ ) in the candidate set, the null hypothesis  $H_0^m: c_m^T \mu = 0$  will be tested against the 1-sided alternative  $H_1^m: c_m^T \mu > 0$  using a multiple contrast test with significance level  $\alpha/2 = 0.025$ , where  $c_m = (c_{m1}, \dots, c_{m5})^T$  is the optimal contrast vector representing model  $m$  and  $\mu = (\mu_1, \dots, \mu_5)^T$  denotes the HiSCR at Week 16 for the applied doses.

Single contrast tests will be used to test the null hypotheses that there is no dose-response signal for candidate model  $m = 1, 2$ . By combining the single test statistics to a multivariate test statistic and comparing this test statistic to a multivariate normal-distribution, the single tests are multiplicity adjusted and the multiple test problem is adequately considered. The maximum of the 2 test statistics will be used as a combined test statistic.

Only if a dose-response signal can be detected for at least 1 of the candidate models in terms of the multiple contrast tests, the shape of the dose-response curve and the target dose(s) of interest will be estimated.

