The MCP-Mod approach as outlined above will be applied to all 20 imputed datasets. If the MCP step results in a non-significant dose-response signal for more than one of the 20 datasets, the results will be considered as not robust enough for dose-response estimation. In this case, the Mod step will not be performed. For the estimation of the dose-response curve for each candidate model (Mod step), the individual model parameters ( $ED_{50}$  for the  $E_{max}$  model and  $ED_{50}$  and  $\delta$  for the logistic model) from the analysis on each imputed dataset will be combined using Rubin's rule.

The percentage of subjects with a response on the basis of the HiSCR (Section 8.2.2.2) determined at Week 12 before administration of IMP will be analyzed in the same way as the primary endpoint.

For all other continuous efficacy endpoints, the absolute values and changes from baseline (absolute and relative) will be summarized by display of basic descriptive statistics (e.g., number of observations (n), mean, standard deviation, minimum, median, maximum, lower quartile, upper quartile, and upper and lower boundary of the 95% CI for the mean) by time point.

Model-based analyses (e.g. analysis of covariance [ANCOVA], Poisson, and logistic regression models) for continuous, count, and binary endpoints will be defined in the statistical analysis plan as deemed necessary and possible.

All categorical efficacy endpoints will be summarized by time point using absolute and relative frequencies including 95% exact CIs based on the binomial distribution.

Sensitivity analyses will be defined for all efficacy endpoints if deemed necessary.

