## **10.10 Handling of Missing Data**

Data imputation rules are defined for missing values for the primary efficacy endpoint of percentage of subjects with a response, as measured by HiSCR at Week 16. Subjects with missing baseline assessments (baseline assessments might be obtained at Screening or at Day 1 before first infusion of IMP) necessary for the calculation of the HiSCR at Week 16 will not be randomized (i.e., there shall be no missing baseline values for HiSCR). Missing values for assessments at Week 16 necessary for the calculation of HiSCR at Week 16 will be replaced by multiple imputation, as described in section [10.5.1](#).

All other missing data will not be replaced.

Sensitivity analyses will be conducted based on the PPS. Further sensitivity analyses (e.g., evaluating patients with missing HiSCR at Week 16 as non-responders) will be defined in the statistical analysis plan if deemed necessary.

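### Section 10.5.1 gives no pooled test statistic or p-value for the primary dose-response test across the 20 imputed datasets, and its 19-of-20 rule costs about 2 to 4 points of power at 3-5% imputed

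*Combined protocol and SAP*

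**What the plan says.** The primary objective (Section 2.1) is "to evaluate a dose-response signal of IFX-1 in subjects with HS according to the HiSCR at Week 16". For a single dataset, Section 10.5.1 defines the test fully: optimal contrasts for an Emax and a logistic model, the larger of the two statistics, and a multivariate-normal reference at 1-sided 0.025. It adds a gate: "Only if a dose-response signal can be detected for at least 1 of the candidate models in terms of the multiple contrast tests" are the curve and target doses estimated.

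Missing Week 16 HiSCR is multiply imputed 20 times, except that discontinuation for relapse, progression or lack of efficacy counts as non-response. MCP-Mod is then applied to each of the 20 datasets. The rule across datasets is: "If the MCP step results in a non-significant dose-response signal for more than one of the 20 datasets", then "the results will be considered as not robust enough for dose-response estimation", and the Mod step is skipped. Rubin's rule appears only for the Mod-step parameters (ED50 for Emax; ED50 and delta for the logistic model).

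The sample size statement in Section 10.2 is that "29 subjects per cohort would yield a power of at least 90% to detect a dose-response signal if present".

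Section 10.10 says "Data imputation rules are defined for missing values for the primary efficacy endpoint" (HiSCR at Week 16) and "All other missing data will not be replaced". Section 10.5.1 nevertheless has Week 12 HiSCR analysed in the same way as the primary endpoint. Section 10.1 defers "extensive details of the statistical analysis methods to be used" to a separate SAP, whose text was not available.

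**The concern.** There are two linked problems.

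1. **No single primary result.** Twenty contrast tests give twenty p-values and nothing combines them. Read literally, the rule on non-significant datasets governs estimation only, so the text does not say whether a signal is declared when 1 to 18 datasets are significant. Read together with the earlier gate, it can be taken as an implicit 19-of-20 rule for the signal, still with no p-value to report. Two competent statisticians could state different primary conclusions from the same data.

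2. **Lost power.** Requiring significance in at least 19 of 20 datasets is stricter than one test on pooled estimates. Under either reading, the trial reaches the curve, the MED and the ED50 less often than it needs to. The 90% in Section 10.2 describes a single contrast test, not the chance of passing this rule.

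**Working it through.** **Inputs from the documents.** HiSCR rates 25/30/45/55/60% at cumulative doses 0, 2000, 4800, 8000 and 10,800 mg; Emax ED50 3000; logistic ED50 3500 and delta 1100; 1-sided alpha 0.025; 29 evaluable and 35 enrolled per cohort (Section 10.2). 20 imputations and the 19-of-20 rule (Section 10.5.1). The full analysis set holds all dosed subjects (Section 10.3), so 35 per cohort is the relevant size once imputation is used.

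**Assumption.** The imputed fraction is not given; the protocol expects it to be relatively small. Of 175 subjects, 3% is about 5 and 5% about 9. The planning allowance of 6 of 35 (17%) is an upper case, because efficacy-related discontinuations are not imputed.

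**Step 1: the plan's own power.**
- Emax shape d/(3000+d): 0, 0.400, 0.615, 0.727, 0.783.
- Logistic shape 1/(1+exp((3500-d)/1100)): 0.040, 0.204, 0.765, 0.984, 0.999.
- Centred and scaled to length 1, the contrasts are (-0.794, -0.165, 0.173, 0.349, 0.436) and (-0.623, -0.440, 0.186, 0.430, 0.447). Their correlation is 0.944, and the bivariate-normal critical value is 2.076.
- Contrast values c'p are 0.284 and 0.300. Standard errors sqrt(sum c²p(1-p)/29) are 0.0845 and 0.0862. The expected statistics are 3.36 and 3.49, giving 93.3% power.
- On the logit scale, power is 88.1-88.7% asymptotically and 90.5-90.9% by simulation. A covariate-adjusted logistic simulation gives 89.9-90.8%.

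The stated figure of at least 90% is reproduced within about 2 points.

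**Step 2: why the rule is stricter.** Let b be the between-imputation variance divided by the within-imputation variance. With imputation by cohort only and a fraction f imputed, b is about f/(1-f). Treat the two highly correlated contrasts as one statistic.
- The pooled test needs the mean statistic to exceed 2.076·sqrt(1+1.05b), where 1.05 = 1+1/20.
- The rule needs the second smallest of 20 statistics to exceed 2.076. That value lies about 1.40 between-imputation SDs below the mean (normal quantile of (2-0.375)/20.25 = 0.080), so the mean must exceed 2.076 + 1.40·sqrt(b).
- Complete-data power at 35 per cohort is 95.1% (logit simulation), so the expected statistic is 2.076 + 1.655 = 3.731. The SD of the mean statistic is sqrt(1+1.05b).

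| Imputed | b | Pooled threshold | Rule threshold | Pooled power | Rule power |
|---|---|---|---|---|---|
| 3% | 0.031 | 2.109 | 2.322 | 94.5% | 91.7% |
| 5% | 0.053 | 2.133 | 2.397 | 94.0% | 90.3% |
| 10% | 0.111 | 2.194 | 2.543 | 92.7% | 87.0% |

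**Step 3: simulation with covariates and prior visits.** HiSCR was generated at 8 visits from a latent normal, with Hurley stage, antibiotic use and AN count as covariates. Imputation was sequential logistic on cohort, covariates and all prior visits (M = 20). The main set-up used exchangeable correlation 0.7, dropout uniform over Weeks 4-16 and 10,000 runs. Correlations, covariate effects and earlier-visit rates are assumed. The ranges cover seven correlation and dropout set-ups (six at 17%).

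| Imputed | Pooled | Rule | Loss, range | Rule power, range |
|---|---|---|---|---|
| 3% | 95.2% | 93.1% | 1.8-2.7 | 92.3-93.3% |
| 5% | 94.6% | 91.7% | 2.5-3.6 | 90.8-92.3% |
| 10% | 93.7% | 88.9% | 4.2-5.6 | 88.0-90.4% |
| 17% | 92.1% | 85.3% | 6.7-7.8 | 82.7-86.2% |

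Simpler simulations without covariates, and with at most one prior-visit predictor, give losses of 2.2-2.8 points at 3% and 2.9-4.1 at 5%. The least favourable puts the rule at 89.6% at 5% imputed. Monte Carlo standard errors in the main work are 0.2-0.5 points.

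**Step 4: type I error.** With 40% response in all cohorts and 5%, 10% and 17% imputed, the rule gives 1.4%, 1.1% and 1.0%; pooling gives 2.3%, 2.2% and 2.2%. With 25% in all cohorts and 10% imputed, the figures are 0.9% and 1.8%. The rule passed while the pooled test failed in at most 0.01% of simulated trials.

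**Step 5: how often the readings diverge.** Trials with 10 to 18 significant datasets make up 2.2-3.0% at 3% imputed and 3.1-4.4% at 5%. In the simplest simulation, 1 to 18 significant datasets occurred in 5.3% and 7.9% of trials.

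**The case against.** The rule is prespecified, conservative and has a stated purpose: not to fit a curve when the evidence depends on the imputation draw. It adds no false positives. At 3-5% imputed, its power is at or above 90% in nearly every set-up, and Section 10.2 never promised 90% power to reach estimation. The two gates together settle whether the Mod step runs for every count of significant datasets. The SAP may name a pooled p-value.

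Much of this stands. At small imputed fractions the loss is modest, and the 10% and 17% rows go beyond what the protocol expects. A further case, in which 29 per cohort already includes imputed subjects (88.8% pooled versus 84.4% rule at 5%), is strained because the full analysis set keeps every dosed subject; it carries little weight here.

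Two things are not answered. Fixing when estimation proceeds does not fix which p-value answers the primary objective. And the extra strictness buys no needed error control, since the pooled test stayed below 2.5% in every null scenario run.

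**Conclusion.** The concern holds. The available text defines no pooled statistic or p-value for the primary test and leaves the status of the 19-of-20 rule open. Against one Rubin-pooled contrast test, the rule loses about 2 to 4 points of power at 3-5% imputed with 35 per cohort, and more as the imputed fraction grows. This rests on the planning response rates, on assumed imputed fractions and on assumed correlation between visits; other reasonable set-ups can move the power figures by 1-2 points. Type I error is not inflated. The missing p-value is the stronger ground for changing the text, subject to what the unseen SAP says. It should be fixed before unblinding. Whether imputation applies to Week 12 HiSCR is a smaller, separate inconsistency between Sections 10.5.1 and 10.10.

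**What to change.** In Section 10.5.1 and the SAP:

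- Fit the covariate-adjusted model in each imputed dataset, and pool the five cohort estimates and their covariance matrix by Rubin's rules.
- Run one multiple contrast test on the pooled estimates and report its adjusted p-value as the primary result.
- If it is significant, fit the Emax and logistic models, including location and scale, to the pooled estimates and derive ED50 and MED from them.
- Report the number of significant datasets as a description of robustness only.
- State whether Week 12 HiSCR is imputed, and use the pooled test there only if it is.

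If the 19-of-20 rule is kept, say whether it decides the signal, name the p-value to be reported, and give its power at, for example, 3%, 5% and 10% imputed.

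The cost is wording and slightly more programming, with no extra subjects or data. The downside is that the robustness count no longer blocks estimation.

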### **10.5.2 Safety**

Treatment-emergent AEs will be analyzed according to the number and percentage of subjects who had a TEAE, as well as the number of TEAEs with the respective MedDRA System Organ Class and Preferred Term. Additionally, the number and percentage of subjects with TEAEs will be further grouped by severity and causal relationship. The number and percentage of subjects with SAEs and AESIs and the number of SAEs and AESIs will be analyzed. Where AEs are grouped by severity or relationship, the maximum severity/relationship per subject and class of AE will be considered. If the number of subjects discontinuing treatment or discontinuing the study is substantial, further analyses taking into account the time of AE onset and cumulative dose may be considered.

Safety laboratory, physical examination, and vital signs parameters will be analyzed by summary statistics (e.g., number of observations, mean, standard deviation, minimum, median, maximum, lower quartile, upper quartile) for absolute values and changes from baseline by visit.

Categorical safety parameters will be summarized by absolute and relative frequencies by time point.

### **10.5.3 Pharmacokinetics**

The analysis of derived PK parameters will be described in a separate PK analysis plan.

### **10.5.4 Pharmacodynamics**

Where applicable, the absolute values and changes from baseline of PD endpoints will be summarized using descriptive statistics (e.g., number of observations (n), mean, standard

---

deviation, minimum, median, maximum, lower quartile, upper quartile, geometric mean) by time point.

All PD parameters will be analyzed based on the FAS with all values and assessments available. Some analyses may be repeated for the PPS.

## **10.6 Demographics and Baseline Characteristics**

Baseline characteristics and demographic information (including medical/HS history and surgeries) will be summarized by cohort and overall. A baseline measurement will be defined as the latest measurement obtained prior to the first administration of IMP, if applicable.

## **10.7 Prior and Concomitant Therapies**

Prior and concomitant therapies will be summarized by absolute and relative frequencies by cohort and overall. Therapies will be defined as concomitant if the start or end date is later than the date of first IMP administration, or if no end date is available (ongoing therapy).

## **10.8 Subject Disposition**

The disposition of subjects who were enrolled (i.e., signed the informed consent form) in the study as well as reasons for discontinuation from study and from treatment will be summarized for each cohort.

## **10.9 Treatment Exposure**

The administration of IMP will be summarized by cohort and will include the number and percentage of subjects completing each treatment visit. The actually received cumulative dose in mg relative to the planned cumulative dose will be calculated per subject and will be summarized for each cohort.

## **10.10 Handling of Missing Data**

Data imputation rules are defined for missing values for the primary efficacy endpoint of percentage of subjects with a response, as measured by HiSCR at Week 16. Subjects with missing baseline assessments (baseline assessments might be obtained at Screening or at Day 1 before first infusion of IMP) necessary for the calculation of the HiSCR at Week 16 will not be randomized (i.e., there shall be no missing baseline values for HiSCR). Missing values for assessments at Week 16 necessary for the calculation of HiSCR at Week 16 will be replaced by multiple imputation, as described in section [10.5.1](#).

All other missing data will not be replaced.

Sensitivity analyses will be conducted based on the PPS. Further sensitivity analyses (e.g., evaluating patients with missing HiSCR at Week 16 as non-responders) will be defined in the statistical analysis plan if deemed necessary.

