Statistical methods	
A total of 175 subjects are planned to be enrolled into the study (i.e., 35 subjects per cohort) to achieve at least 29 subjects per cohort available for the primary analysis of the primary efficacy endpoint. The sample size is selected so that the multiple contrast test (as part of the multiple comparisons procedure-modelling [MCP-Mod] that will be used to analyze the primary efficacy endpoint) exceeds a power of 90%. With the planned sample size, the power criterion of the multiple contrast test is fulfilled because 29 subjects per cohort would yield a power of at least 90% to detect a dose-response signal if present. A 1-sided significance level of <math>\alpha = 0.025</math> will be used.
 
In general, data will be analyzed by cohort and study phase (Main Period and Extension Period) and may be differentiated further (e.g., by visit or by study site).
 
The primary efficacy endpoint of the percentage of subjects with HiSCR at Week 16 will be analyzed using the MCP-Mod procedure.
 
The secondary efficacy endpoint of the percentage of subjects with HiSCR at Week 12 will be analyzed in the same way as the primary endpoint using the MCP-Mod procedure.
 
For all other continuous efficacy endpoints, the absolute values and changes from baseline (absolute and relative) will be analyzed by descriptive statistics (e.g., number of observations, mean, standard deviation, minimum, median, maximum, lower quartile, upper quartile, and upper and lower boundary of the 95% confidence interval [CI] for the mean) by time point. Model-based analyses (e.g., analysis of covariance [ANCOVA], Poisson, and logistic regression models) for continuous, count, and binary endpoints will be defined in the statistical analysis plan as deemed necessary and possible.
 
All categorical efficacy endpoints will be summarized by time point using absolute and relative frequencies, including 95% exact CIs based on the binomial distribution.
 
Sensitivity analyses will be defined for efficacy endpoints if deemed necessary.
 
Continuous safety parameters will be analyzed by descriptive statistics for absolute values and changes from baseline (absolute and relative) by time point. Categorical safety parameters will be summarized by absolute and relative frequencies by time point.
 
No formal interim analysis is planned for this study.
 
An independent, unblinded Data Monitoring Committee (DMC) will be established to allow regular monitoring of the study data in order to detect and report early evidence of unanticipated harm to subjects.

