The estimated dose-response curve will be used to estimate the MED and  $ED_{50}$ . The MED is defined as the minimum dose, at which the HiSCR at Week 16 is at least 15% higher than the HiSCR at Week 16 in the placebo group. An improvement of 15% over placebo in HiSCR at Week 16 is considered as clinically relevant [15]. The  $ED_{50}$  is defined as the minimum dose that achieves 50% of the maximum achievable effect over placebo. Standard formulas for the estimation of  $ED_{50}$  will be used and will be explicitly stated in the statistical analysis plan.

Multiple imputations will be performed for subjects with missing data on HiSCR at Week 16 who did not discontinue before Week 16 because of one of the following reasons:

- Disease relapse
- Progressive disease
- Lack of efficacy

Subjects who discontinued before Week 16 because of one of the above mentioned reasons will be treated as not having achieved HiSCR at Week 16. All further specifications for multiple imputations are based on the assumption that the number of subjects that need to have the HiSCR at Week 16 imputed, will be relatively small.

Multiple imputations will be performed based on the assumption that HiSCR response at Week 16 is missing at random, i.e. missingness will not depend on the HiSCR at Week 16 itself but will only depend on the factors in the imputation model. The factors that will be used in the multiple imputation model for HiSCR at Week 16 are HiSCR at prior visits, cohort, baseline Hurley Stage, baseline AN count, and concomitant use of antibiotics. We anticipate that baseline Hurley Stage, baseline AN count and concomitant use of antibiotics will not be

---

missing for subjects in the intent-to-treat population. The multiple imputation model will be using fully conditional specification logistic regression. We will perform 20 imputations using a random seed of 122007 using SAS PROC MI.

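### Section 10.10 replaces no missing data except Week 16 HiSCR, which leaves the Week 12 HiSCR rule open and lets known failures drop out of the Extension by-visit response percentages

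*Combined protocol and SAP*

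**What the plan says.** **Missing data.** Section 10.10 limits imputation to HiSCR at Week 16, refers to 10.5.1 for the method, and closes the rest with "All other missing data will not be replaced". Section 8.2.2.2 records HiSCR as missing when any of its three components is missing.

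**Primary method (10.5.1).** It has three parts.
- Subjects who discontinue before Week 16 for relapse, progression or lack of efficacy "will be treated as not having achieved HiSCR at Week 16".
- Other missing Week 16 responses are multiply imputed, with 20 datasets.
- A condition on the imputed datasets: "If the MCP step results in a non-significant dose-response signal for more than one of the 20 datasets", the modelling step is not done.

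**Week 12 HiSCR.** In 10.5.1 the percentage "determined at Week 12 before administration of IMP will be analyzed in the same way as the primary endpoint". The Synopsis adds a qualifier: "HiSCR at Week 12 will be analyzed in the same way as the primary endpoint using the MCP-Mod procedure".

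**Extension Period.** Section 10.4.1 carries the by-time-point endpoints into the Extension, grouped by Week 16 responder status. HiSCR and the 50% reduction in abscess and inflammatory nodule (AN) count are on the exploratory list. Under 10.5.1, categorical efficacy endpoints are "summarized by time point using absolute and relative frequencies including 95% exact CIs". Sections 5.4.2 and 6.2.2 discontinue Week 16 responders with persisting loss of response and Week 16 non-responders with WOAI. Section 10.4.1 also has a loss-of-response percentage whose denominator is all Week 16 responders.

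**The concern.** Week 12 HiSCR is tested by MCP-Mod, so its missing-data rule should be settled before unblinding. As written, a subject who leaves before Week 12 for lack of efficacy may be a failure or may be absent, depending on which section the programmer follows.

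In the Extension, the protocol removes subjects because of the outcome that is then tabulated. If their later visits are simply missing and the percentages use observed cases, each removal raises the displayed response rate. Evaluating long-term efficacy is a stated secondary objective (2.2), and these tables are its main descriptive evidence. There is no concurrent placebo group against which a reader could notice the distortion.

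**Working it through.** **1. The plan's own figure.** Section 10.2 states power of at least 90% with 29 per cohort, one-sided alpha 0.025, and rates of 25/30/45/55/60% at cumulative doses 0/2000/4800/8000/10,800 mg. Contrasts from the Emax shape (ED50 3000) and the logistic shape (ED50 3500, delta 1100) give a critical value of about 2.08. Power is then 88.1% to 88.7% on the logit scale, 89.7% with a common variance, and 93.0% to 93.3% on the probability scale with unpooled variances. These values bracket 90%, so the set-up is a fair basis for step 3.

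**2. Week 12: the three readings.**

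| Reading | Lack-of-efficacy dropout | Other missing | 20-dataset condition |
|---|---|---|---|
| Full primary method | non-responder | multiply imputed | applies |
| Failure coding only | non-responder | left out | does not arise |
| Available data only | left out | left out | does not arise |

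**3. Week 12: size.** Assumptions: the Week 16 rates hold at Week 12, there are 35 per cohort, and k non-responders per affected cohort drop out for lack of efficacy. Section 10.2 plans 35 per cohort to keep 29, so k = 6 is an upper bound.

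With non-responder coding, top cohort minus placebo is 60.0 - 25.0 = 35.0 points. With available data:
- Dropouts in placebo only: 0.60 - 8.75/(35-k), where 8.75 = 0.25 × 35. This gives 34.3, 33.5, 32.7 and 29.8 points for k = 1, 2, 3 and 6.
- Dropouts in every cohort: 0.35 × 35/(35-k). This gives 36.0, 37.1, 38.3 and 42.2 points.

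The direction therefore depends on the dropout pattern. The MCP step was simulated with 8,000 trials per scenario, using unadjusted logits with 0.5 added to the responders and 1 to n:

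| Dropouts | Power, non-responder coding | Power, available data | Decisions that differ |
|---|---|---|---|
| 3 in every cohort | 94.4% | 95.0% | 0.6% |
| 6 in every cohort | 94.9% | 95.9% | 1.3% |
| 3 in placebo only | 94.6% | 90.7% | 3.9% |
| 6 in placebo only | 94.9% | 84.9% | 10.0% |

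A repeat with 40,000 trials gave 0.7%, 1.2%, 4.0% and 9.7%. With dropouts in proportion to non-response (1 to 3 in placebo, scaled elsewhere), about 0.5% to 1.5% of decisions differ. The simulation has lack-of-efficacy dropouts only, so the first two readings coincide in it. It does not include imputation, the 20-dataset condition or the covariates.

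**4. Extension: removed subjects are failures.** HiSCR requires AN ≤ Baseline/2. Loss of response means AN > (Baseline + Week 16)/2. Because the Week 16 count is at least 0, this implies AN > Baseline/2. WOAI means AN ≥ Baseline. Neither is compatible with HiSCR or with a 50% AN reduction.

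As a check, baseline AN 3 to 60, Week 16 AN 0 to half of baseline, and current AN 0 to 120 give 91,212 combinations that meet loss of response. None has a 50% reduction, but 4,735 have a 25% reduction. For example, baseline 10 and Week 16 count 2 give a threshold of 6. A current count of 7 is loss of response, yet a 30% reduction. So removal for loss of response does not imply HiSCR25 failure.

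**5. Extension: size.** Let N be the stratum size, x the responders at a later visit, and f the share removed. Over the full stratum the rate is x/N. With observed cases it is x/(N(1-f)), so the ratio is 1/(1-f). The documents do not give f.

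| f (assumed) | Factor | A full-stratum rate of 30% (assumed) is shown as |
|---|---|---|
| 5% | 1.05 | 31.6% |
| 10% | 1.11 | 33.3% |
| 20% | 1.25 | 37.5% |
| 30% | 1.43 | 42.9% |

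For scale, the planning rates imply 35 × (0.25 + 0.30 + 0.45 + 0.55 + 0.60) = 75.25 responders and 99.75 non-responders at Week 16, before any dropout. In a stratum of 100 with f = 20%, 30/100 would be printed as 30/80.

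**The case against.** **Week 12.** A reader might infer that 10.5.1 and 10.10 cannot both be applied. The documents do not support that. Section 10.5.1 separates failure coding from imputation, and for Week 16 section 10.10 describes replacement only as multiple imputation. Week 12 could therefore keep the failure coding and skip imputation, and the differences in decision modelled above would be zero. The Synopsis wording also allows the test alone to carry over. For one dataset, 10.5.1 already supplies a complete rule: "Only if a dose-response signal can be detected for at least 1 of the candidate models", the curve is estimated. The Week 12 sentence directly follows the imputation text, so the specific text could also be held to govern the general line. All of this stands, and it shows several workable readings without choosing one.

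**Extension.** No section states an observed-case denominator. That follows only from combining 8.2.2.2 with 10.10, and exact endpoint definitions are left to a statistical analysis plan (10.1) that is not in the text reviewed. This stands, so the point is conditional. Counts are reported as well as percentages, so a reader who knows the stratum size could rebuild the rate. The printed percentages and intervals would still use the reduced denominator.

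Other sources help only in part. The loss-of-response percentage covers Week 16 responders, not WOAI in non-responders. Section 10.8 tabulates discontinuation reasons by cohort, not by Week 16 stratum. The early-discontinuation and 3-month post-treatment visits collect lesion data, but they do not stand in for the later planned Extension visits.

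**Number of visits lost.** A reader might try to count the visits that a removed subject misses. The documents do not support a single count. Section 7.3 ties removal for loss of response to the optional visit, while 6.2.2 ties it to the next planned visit. The WOAI definition already contains two consecutive visits, and 5.4.2 and 6.2.2 ask for two consecutive visits again. These passages must be reconciled.

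**Conclusion.** The point holds as an inconsistency on one secondary endpoint and a gap in exploratory tables.

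- **Week 12:** the rule is unsettled between three readings. The practical effect is probably small, about 1% discordant decisions with dropouts spread over the cohorts. The 3.9% and 10.0% figures need every such dropout to be in placebo. A reader might take those as the expected effect, but nothing in the documents suggests that pattern. Week 12 rates and dropout counts are assumptions.
- **Extension:** if observed cases are used, HiSCR and 50% AN-reduction percentages are overstated by 1/(1-f) relative to counting removed failures as non-responders at later visits. Both f and the denominator are assumptions.

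A reader might also infer that the main conclusion is at risk. It is not: the Week 16 primary analysis has its own rules, and no treatment contrast rests on the Extension tables. The change is worth making because it is cheap and the alternative favours the drug.

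**What to change.** **(a) Week 12.** Amend 10.10 so that the failure coding, multiple imputation and 20-dataset condition used at Week 16 also apply to Week 12 HiSCR, with discontinuation judged before Week 12. If another reading is intended, 10.5.1 and 10.10 should both say so.

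**(b) Extension.** In 10.10 or the statistical analysis plan:
- Report by-visit HiSCR and 50% AN reduction over all subjects in each Week 16 stratum.
- Count subjects discontinued for loss of response, WOAI or lack of efficacy as non-responders at later visits, and state how subjects missing for other reasons are counted.
- Keep observed-case tables as supportive.
- State a separate rule for HiSCR25, because loss of response in a Week 16 responder does not imply HiSCR25 failure.

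**(c) Removal rules.** Reconcile the passages on the timing of removal for loss of response (6.2.2 and 7.3) and for WOAI (Definition of Terms, 5.4.2 and 6.2.2), so that removed subjects can be identified without ambiguity.

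**Cost.** A few sentences and some table programming, settled before unblinding. The reported long-term rates become less favourable.
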